1.2. Study Design

1.2.1. JNJ-77242113PSO2001

This is a randomized, double-blind, placebo-controlled, dose-ranging, parallel group, multicenter, interventional study in participants with moderate-to-severe plaque psoriasis.

A target of 240 participants will be enrolled in this study with 40 participants planned per intervention group.

Participants will be instructed to take the study intervention in the morning (AM) and in the evening (PM) on an empty stomach with approximately 240 mL of noncarbonated water at approximately the same time every day. An empty stomach is defined as abstaining from food intake for at least 2 hours before taking the study intervention and abstaining from food and liquid intake for at least 30 min after taking the study intervention. Dietary intake should be recorded per study manual.

The study intervention may be delivered directly to the participants from a courier as permitted by local requirements and/or regulations if approved by the Independent Ethics Committee (IEC)/ Institutional Review Board (IRB); Section 6.2 of the protocol. Details regarding delivery are provided in the study manual. The participant has the ability to opt-in or opt-out of using this service throughout the duration of the study.

Group 1: JNJ-77242113 (25 mg QD): Participants will receive JNJ-77242113 25 mg QD from Week 0 through Week 16

Group 2: JNJ-77242113 (50 mg QD): Participants will receive JNJ-77242113 50 mg QD from Week 0 through Week 16

Group 3: JNJ-77242113 (100 mg QD): Participants will receive JNJ-77242113 100 mg QD from Week 0 through Week 16

Group 4: JNJ-77242113 (25 mg BID): Participants will receive JNJ-77242113 25 mg BID from Week 0 through Week 16

Group 5: JNJ-77242113 (100 mg BID): Participants will receive JNJ-77242113 100 mg BID from Week 0 through Week 16

Group 6: Placebo: Participants will receive placebo BID from Week 0 through Week 16

[figure not shown]
At Week 16, eligible participants will have the option to enroll in a 36-week treatment long term extension (LTE) study; all participants will be treated with active study intervention in the LTE (77242113PSO2002).

For JNJ-77242113PSO2001 study, one planned database lock (DBL) will occur at Week 16. Two interim analyses will occur in this study at Week 4 and Week 16, respectively.

At the time of the 77242113PSO2001 Week 16 DBL, Sponsor will be unblinded to perform the analyses and Phase 3 planning. Select Sponsor personnel will be unblinded to the individual treatment assignments, while others will only be unblinded to group level summaries. Details of the unblinding plan will be documented prior to DBL and unblinding. Investigators and sites will remain blinded until the end of 77242113PSO2002 (LTE study) study and the final database lock of the 77242113PSO2002 study.

For the interim analyses, group level summaries will be unblinded to Interim Analysis Committee (IAC) and the individual treatment assignment information will be unblinded to the Statistical Supporting Group (SSG) for analyses. The study team will not be unblinded to either the group level summaries or the individual treatment assignments at this time. The SSG and IAC must keep the treatment assignment information confidential until the study unblinding at the 77242113PSO2002 study Week 16 DBL or termination of the study. The investigator sites and participants will continue to be blinded to treatment assignment until the final database lock from 77242113PSO2002.

A diagram of the study design is provided in [Figure 1](#).

Figure 1: Schematic Overview of 77242113PSO2001

BID = twice daily LTE = Long-term extension QD = once daily (R) = Randomization

^a The LTE will be detailed in a separate protocol (77242113PSO2002). All eligible participants who enroll in the LTE will transition to the LTE protocol for further visit instructions.

^b All ineligible participants for the LTE and eligible participants for the LTE who choose not to enroll in the LTE will complete 4 weeks of safety follow-up to complete the study.

^c Final safety follow-up for participants who do not enter the LTE.

3896_v3

1.2.2. JNJ-77242113PSO2002

JNJ-77242113PSO2002 study is a multicenter, LTE, double-blind, dose-ranging, parallel group, interventional study in participants with moderate-to-severe plaque psoriasis.

All eligible participants from Protocol 77242113PSO2001 will be given the option to enroll in this LTE study, JNJ-77242113PSO2002.

All participants randomized to an active JNJ-77242113 dose regimen (25 mg QD, 50 mg QD, 100 mg QD, 25 mg BID, or 100 mg BID) in Protocol 77242113PSO2001 will continue to receive the same dosing regimen of JNJ-77242113 in this study in a blinded manner. Participants randomized to placebo in Protocol 77242113PSO2001 will receive JNJ-77242113 100 mg QD starting at Week 0 through the end of the treatment period in this study.

If the Week 0 visit for this study takes place on a different day as the Week 16 visit of study 77242113PSO2001, the sponsor and medical monitor must be notified. Approval from the medical

monitor or designee is required to enroll participants into study 77242113PSO2002 with a gap in study intervention administration between study 77242113PSO2001 and 77242113PSO2002.

The following JNJ-77242113 dosing regimens will be studied in this protocol:

Group 1: JNJ-77242113 (25 mg QD): Participants will receive JNJ-77242113 25 mg QD from Week 0 through Week 36

Group 2: JNJ-77242113 (50 mg QD): Participants will receive JNJ-77242113 50 mg QD from Week 0 through Week 36

Group 3: JNJ-77242113 (100 mg QD): Participants will receive JNJ-77242113 100 mg QD from Week 0 through Week 36

Group 4: JNJ-77242113 (25 mg BID): Participants will receive JNJ-77242113 25 mg BID from Week 0 through Week 36

[figure not shown]
Group 5: JNJ-77242113 (100 mg BID): Participants will receive JNJ-77242113 100 mg BID from Week 0 through Week 36

Group 6: Placebo → JNJ-77242113 (100 mg QD): Participants originally randomized to placebo in Protocol 77242113PSO2001 will receive JNJ-77242113 100 mg QD from Week 0 through Week 36

One planned database lock (DBL) will occur at Week 40. The study protocol may be amended at the sponsor's decision to extend the treatment period to provide participants access to one or more of the JNJ-77242113 doses. No formal interim analyses are planned for this study. However, selected efficacy, safety, and other data through Week 36 of this LTE study may be included in the interim analyses of the originating study (77242113PSO2001) for those participants who have entered the LTE study when the interim analyses occur. In addition, selected efficacy, safety, and other data through Week 36 of this LTE study may be included in the Week 16 DBL of the originating study (77242113PSO2001) for those participants who have entered the LTE study when the Week 16 DBL occur.

An external Independent Data Monitoring Committee (iDMC) has been commissioned for study 77242113PSO2001 and this study (77242113PSO2002) to review the safety data at an ongoing basis.

A diagram of the study design is provided in [Figure 2](#).

Figure 2: Schematic Overview of 77242113PSO2002

^a Participants who have completed study 77242113PSO2001 through Week 16 may be eligible to participate in this LTE study. All participants who were originally randomized to a JNJ-77242113 active dosing arm in study 77242113PSO2001 and enroll in this LTE study will continue to be treated with their assigned dosing regimens from study 77242113PSO2001 in a blinded manner. All participants who were originally randomized to placebo in study 77242113PSO2001 will receive JNJ-77242113 100 mg QD starting at Week 0 through the end of this LTE study in a blinded manner.

BID = twice daily; LTE = long-term extension; QD = once daily

3695_v5

2. STATISTICAL HYPOTHESES

2.1. 77242113PSO2001

The hypothesis of this study is that there is a dose response relationship for JNJ-77242113 in the proportion of participants achieving a PASI 75 response at Week 16 in participants with moderate to severe psoriasis disease.

The null hypothesis to be tested is that there is no dose-response for the JNJ-77242113 doses and placebo in proportion of participants achieving a PASI75 response at Week 16 in participants with moderate to severe psoriasis disease.

2.2. 77242113PSO2002

The objective of this LTE study is to evaluate the long-term clinical response and safety of JNJ-77242113 treatment in participants with moderate-to-severe psoriasis. All of the analyses will be descriptive in order to evaluate the longer-term effects of efficacy and safety and no statistical hypothesis is specified.

3. SAMPLE SIZE DETERMINATION

3.1. 77242113PSO2001

This study is designed to enroll approximately 240 participants, in order to provide sufficient data to have adequate power to detect a JNJ-77242113 dose-response signal for the proportion of participants achieving PASI 75 at Week 16 using the Multiple Comparison Procedures with modeling techniques (MCP-Mod) method.

The sample size of 240 participants was also chosen in order to have sufficient power to detect a difference between the JNJ-77242113 groups and the placebo group for the primary endpoint of the proportion of participants achieving PASI 75 at Week 16.

The assumptions for the sample size and power calculations specified below were mainly based on the clinical data from the guselkumab Phase 2 and Phase 3 clinical studies that evaluated the safety and efficacy of guselkumab in the treatment of adult participants with moderate-to-severe plaque psoriasis.

The null hypothesis of no dose-response relationship is to be tested at an overall Type 1 error rate of 0.05 (2-sided). Assuming a PASI 75 response rate of 6% and 80% in the placebo and JNJ-77242113 highest dose groups, respectively, a sample size of approximately 40 participants in the placebo group and each of the JNJ-77242113 treatment groups will provide an average power of at least 95% to detect a dose-response signal across different candidate dose-response models. [Table 1](#) and [Table 2](#) below show the candidate dose response models and the power to detect a dose-response signal based on the primary endpoint of the proportion of participants achieving PASI 75 at Week 16 for various candidate models.

Table 1: Candidate Dose-response^a Models

Model Type	Model specification ^b
E _{max} 1	dose/(35+dose) (ED ₅₀ =35)
E _{max} 2	dose/(50+dose) (ED ₅₀ =50)
Logistic	1/{1+exp[(35-dose)/15]} (ED ₅₀ =35, δ=15)
SigEMax	Dose ³ /((35) ³ +dose ³) (ED ₅₀ =35, h=3)
Linear	dose
Quadratic	dose-0.002*(dose**2) (δ=-0.002)

^a Response is PASI 75 response at Week 16.
^b A standardized version of the dose response model

Table 2: Summary of powers for each candidate models

Sample size Per Group	Emax 1	Emax 2	Logistic	SigEMax	Linear	Quadratic	Mean Power
40	>95%	>95%	>95%	>95%	>95%	>95%	>95%

Furthermore, assuming PASI 75 response rates at Week 16 are 5% to 10% for placebo, 30% to 80% for the JNJ-77242113 dose groups, respectively, with 40 participants in each of the treatment groups, approximately 240 participants are planned to be randomized in equal ratio to the placebo and each of JNJ-77242113 dose groups (n=40/arm), this study provides:

At least 90% power to detect a 35% treatment difference between the JNJ-77242113 treatment groups (n=40) and the placebo group (n=40) in the proportion of participants who achieve a PASI 75 response at Week 16 at a significant level of 0.05 (2-sided) based on a 2-sample Z-test.

3.2. 77242113PSO2002

Protocol 77242113PSO2002 is the LTE study of Protocol 77242113PSO2001, therefore there is no formal calculation of the sample size for study 77242113PSO2002. The sample size of this LTE study will be determined by the number of participants who enroll in study 77242113PSO2001 and are eligible to enter and choose to participate in this LTE study.

4. POPULATIONS (ANALYSIS SETS) FOR ANALYSIS

Unless specified otherwise, data included in the analyses for both studies are briefly summarized below:

4.1. 77242113PSO2001

All data available through Week 16 database lock of the 77242113PSO2001 study will be included. The populations for analysis are defined in [Table 3](#) below.

Table 3: Populations for Analyses for 77242113PSO2001

Population	Description
Enrolled	All participants who signed the ICF
Randomized	All participants who were randomized in the study
FAS	All randomized participants who took at least 1 dose of study intervention
Per Protocol (PP)	The per protocol analysis set (PP) includes a subset of participants in the full analysis set (FAS) who were in compliance with the protocol. Compliance is defined as participants in FAS and meet the following criteria: 
 • Has a total BSA $\geq 10\%$ at the screening and baseline visit. • Has a total PASI score ≥ 12 at the screening and baseline visit • Has a total IGA score ≥ 3 at the screening and baseline visit • Received all scheduled treatment and with overall compliance of study treatment at least 80% prior to Week 16, Or participants who did not complete all scheduled study intervention administration due to intercurrent events (i.e., discontinued the study intervention due to lack of efficacy, an AE of worsening of psoriasis, or started a protocol-prohibited medication or therapy during the study that could improve psoriasis)
Safety Analysis Set	All randomized participants who took at least 1 dose of study intervention
PK Analysis Set	All randomized participants who received at least 1 complete dose of JNJ-77242113 and had at least 1 valid blood sample drawn for PK analysis after their first dose of JNJ-77242113
Immunogenicity Analysis Set	All randomized participants who received at least 1 dose of JNJ-77242113 and who had at least 1 sample obtained after the first dose of JNJ-77242113 for the detection of antibodies to JNJ-77242113
PD Analysis Set	All randomized participants who received at least 1 complete dose of JNJ-77242113

4.2. 77242113PSO2002

For selected subject's information and all safety analyses, combined data from 77242113PSO2001 and 77242113PSO2002 studies for participants initially randomized to JNJ-77242113, and who crossed over and received JNJ-77242113 for participants initially randomized to placebo will be included. In addition, safety data from 77242113PSO2002 data will also be summarized for randomized participants in 77242113PSO2001 who entered the long-term extension study 77242113PSO2002 and received at least one dose of study intervention (including a partial dose) during the 77242113PSO2002 study period. For efficacy and PK/PD analyses, efficacy and PK/PD data from 77242113PSO2001 and 77242113PSO2002 studies will be included and summarized.

The populations for analysis are defined in [Table 4](#) below.

Table 4: Population for analysis for 77242113PSO2002

Population	Description
FAS	Randomized participants who received at least one dose of study intervention in the originating study (77242113PSO2001) for participants initially randomized to JNJ-77242113, and participants who crossed over and received JNJ-77242113 for participants initially randomized to placebo
Safety Analysis Set	Randomized participants who received at least one dose of study intervention in the originating study (77242113PSO2001) for participants initially randomized to JNJ-77242113, and participants who crossed over and received JNJ-77242113 for participants initially randomized to placebo
LTE Safety Analysis Set	The LTE safety analysis set consists of randomized participants in 77242113PSO2001 who entered the long-term extension study 77242113PSO2002 and received at least one dose of study intervention (including a partial dose) during the 77242113PSO2002 study period
PK Analysis Set	All participants in 77242113PSO2001 or 77242113PSO2002 who received at least 1 complete dose of JNJ-77242113 and had at least 1 valid blood sample drawn for PK analysis after their first dose of JNJ-77242113
Immunogenicity Analysis Set	All participants in 77242113PSO2001 or 77242113PSO2002 who received at least 1 dose of JNJ-77242113 and who had at least 1 sample obtained after the first dose of JNJ-77242113 for the detection of antibodies to JNJ-77242113

Unless otherwise specified, all over-time (e.g., Week 0-52) efficacy analyses will be based on the Full Analysis Set (FAS), and safety analyses with cumulative safety data by combining studies JNJ-77242113PSO2001 and JNJ-77242113PSO2002 will be based on the Safety Analysis Set. All LTE-specific safety analyses (include data only from JNJ-77242113PSO2002 study) will be based on the LTE Safety Analysis Set.

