Safety results from PN-235-01 show that JNJ-77242113 was well tolerated with no significant safety signals or concerns identified. There were no deaths or SAEs reported. The final cohort of the MAD (1000 mg QD) was interrupted after a preliminary echocardiogram for a single participant was misread and on final report was deemed to be normal. At the time the study was interrupted, in the 1000 mg QD cohort, 8 participants had completed 8 out of the planned 10 days of treatment, and 2 participants had completed 7 days of treatment.

Refer to the JNJ-77242113 IB for the most up to date safety information from this clinical study.

Pharmacokinetic Summary

Preliminary PK data from FIH study PN-235-01 indicate that systemic exposure (C_{max} and AUC) to JNJ-77242113 is approximately dose proportional across the dose range evaluated to date. After multiple QD dosing, steady state was achieved by Day 7 (earliest timepoint evaluated), with minimal drug accumulation consistent with the observed mean terminal phase half-life of approximately 9 to 12 hours.

Interim results from an ongoing, multipart, randomized, open-label, single-dose, crossover study in healthy participants (77242113PSO1003) indicate that the oral bioavailability and PK profile of JNJ-77242113 administered under fasted conditions as an immediate-release (IR) tablet formulation is similar to the oral solution used in the FIH study PN-235-01. The PK results also indicate that concomitant food (high calorie, high-fat breakfast) increased the median time to reach t_{max} and significantly reduced the rate (C_{max}) and extent (AUC) of JNJ-77242113 absorption. Based on the interim food effect data from protocol 77242113PSO1003, study intervention should be administered under fasted conditions.

Refer to the JNJ-77242113 IB for more information on human PK.

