4. STUDY DESIGN

4.1. Overall Design

This is a randomized, double-blind, placebo-controlled, dose-ranging, parallel group, multicenter, interventional study in participants with moderate-to-severe plaque psoriasis.

A target of 240 participants will be enrolled in this study with 40 participants planned per intervention group.

Participants will be instructed to take the study intervention in the morning (AM) and in the evening (PM) on an empty stomach with approximately 240 mL of noncarbonated water at approximately the same time every day. An empty stomach is defined as abstaining from food intake for at least 2 hours before taking the study intervention and abstaining from food and liquid intake for at least 30 min after taking the study intervention. Dietary intake should be recorded per study manual.

The study intervention may be delivered directly to the participants from a courier as permitted by local requirements and/or regulations if approved by the Independent Ethics Committee (IEC)/ Institutional Review Board (IRB); Section 6.2. Details regarding delivery are provided in the study manual. The participant has the ability to opt-in or opt-out of using this service throughout the duration of the study.

Group 1: JNJ-77242113 (25 mg QD): Participants will receive JNJ-77242113 25 mg QD from Week 0 through Week 16

Group 2: JNJ-77242113 (50 mg QD): Participants will receive JNJ-77242113 50 mg QD from Week 0 through Week 16

Group 3: JNJ-77242113 (100 mg QD): Participants will receive JNJ-77242113 100 mg QD from Week 0 through Week 16

Group 4: JNJ-77242113 (25 mg BID): Participants will receive JNJ-77242113 25 mg BID from Week 0 through Week 16

Group 5: JNJ-77242113 (100 mg BID): Participants will receive JNJ-77242113 100 mg BID from Week 0 through Week 16

Group 6: Placebo: Participants will receive placebo BID from Week 0 through Week 16

At Week 16, eligible participants will have the option to enroll in a 36-week treatment long term extension (LTE) study; all participants will be treated with active study intervention in the LTE. The study design of the LTE will be detailed in a separate protocol (77242113PSO2002).

The total duration of this study is up to 24 weeks: a screening period of ≤ 4 weeks, a 16-week treatment period, and a 4-week safety follow-up period after the last study intervention administration for participants who are ineligible or have decided to not enroll in the LTE study at

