6.4. Study Intervention Compliance

Participant compliance with study intervention will be assessed at each visit during the treatment period by counting returned tablets.

A participant will be considered noncompliant if he or she misses more than 20% of the prescribed doses of study intervention during the study, unless study intervention is withheld for safety reasons. Similarly, a participant will be considered significantly noncompliant if he or she is judged by the investigator to have intentionally or repeatedly taken 20% or more than prescribed amount of study intervention during the study.

If a participant's study intervention intake is not according to the protocol, the investigator will take the necessary measures to ensure future adherence to the protocol. If necessary, the participant maybe discontinued from study intervention by the investigator or medical monitor (Section 7).

Study intervention compliance will be further detailed in the statistical analysis plan (SAP).

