5.7.1.2. Data Handling Rules

Unless otherwise specified, the following data handling rules will apply to PK sample analyses:

[figure not shown]
- Plasma concentration summaries will be based on the actual treatment received.
- All plasma concentration summaries for a particular timepoint will include data obtained from treated participants at the timepoint of interest without imputing any missing data.
- A concentration not quantifiable (below the lower limit of quantification) will be treated as 0 in the summary statistics and shown as the lower limit of quantification (< LLOQ) in the data listings.
- The data from a participant who discontinued study agent will be excluded from the by-visit data analyses from that point onwards. In addition, the data from a participant who received an incomplete/ incorrect or skipped dose(s) based on 2 previous doses prior to the PK sample collection or data from a participant who skip dose prior to PK sample collection will be excluded for that visit.

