6.7. Appendix 7 Intervention Compliance

Treatment compliance will be assessed based through Week 16 on the full analysis set (FAS) for study 77242113PSO2001 and through Week 52 (Week 36 of the 77242113PSO2002 study) on full analysis set for study 77242113PSO2002. Descriptive summaries (sample size, mean, standard deviation, median, and range) will be presented for the percent of compliance defined as the number of tablets taken divided by the number of tablets that should have been taken. Overall compliance will be categorized as $> 120\%$, 80 to $\leq 120\%$, and $< 80\%$. In addition, treatment compliance will be assessed by summarizing the protocol deviation of the study agent administration related to incorrect study agent or dose received and missed administrations.

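### The per-protocol set has a floor of 80% on tablet compliance but no ceiling, so it keeps over-takers whom the protocol calls significantly noncompliant

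*SAP*

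**What the plan says.** SAP Section 4.1, Table 3, takes the per-protocol set from the full analysis set and states what compliance means there: "Compliance is defined as participants in FAS and meet the following criteria". The list that follows has BSA, PASI and IGA thresholds at screening and baseline, and one treatment item: "Received all scheduled treatment and with overall compliance of study treatment at least 80% prior to Week 16". As an alternative to that item, it admits participants who stopped early for lack of efficacy, for worsening psoriasis reported as an adverse event, or because they started a prohibited therapy that could improve psoriasis.

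Protocol Section 6.4 has a rule on each side. A participant is noncompliant who "misses more than 20% of the prescribed doses of study intervention during the study", apart from doses withheld for safety. A participant is significantly noncompliant if the investigator judges that he or she has "intentionally or repeatedly taken 20% or more than prescribed amount of study intervention during the study".

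SAP Appendix 7 (Section 6.7) defines percent compliance as the "number of tablets taken divided by the number of tablets that should have been taken" and reports it in three bands: above 120%, 80% to 120% inclusive, and below 80%. The bands are descriptive only.

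**The concern.** The SAP's floor of 80% matches the protocol's rule on missed doses. The protocol's rule on excess intake, which carries the stronger label of the two, has no counterpart in Table 3. The compliance measure can exceed 100%, and the SAP already counts participants above 120%, so the information needed for an upper limit is there but is not used.

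A per-protocol analysis is meant to show the effect in people who took the assigned regimen. In a dose-ranging trial, an over-taker in an active arm is analysed under a dose lower than the one taken. As an extreme illustration, a ratio of 2.00 in the 25 mg QD arm means 2 x 25 = 50 mg/day, the daily dose of another arm. If response rises with dose, keeping such participants would flatter the lower arm against placebo. In the placebo arm, over-taking adds no active drug.

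**Working it through.** The plan states no figure on this point, so there is none to reproduce. The check compares the rules and then applies them to a range of ratios.

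**1. The two protocol limits as ratios.** Let c = tablets taken / tablets due (SAP Appendix 7), treating doses and tablets as interchangeable.

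- Missing more than 20% of doses means c < 0.80. Table 3 keeps c >= 0.80, so the lower limit agrees.
- Taking at least 20% too much means c >= 1.20. Table 3 has no matching limit.

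**2. The Table 3 rule against the SAP's own middle band.**

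| c | Table 3 as written (c >= 0.80) | 80% to 120% band (0.80 <= c <= 1.20) |
|---|---|---|
| 0.79 | out | out |
| 0.80 | in | in |
| 1.00 | in | in |
| 1.20 | in | in |
| 1.21 | in | out |
| 1.50 | in | out |
| 2.00 | in | out |

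The rules differ only above 1.20. At exactly 1.20 the band still admits a participant whom the protocol could call significantly noncompliant, because the protocol's limit starts at 20% and the SAP's top band starts above 120%.

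**3. Scale.** Two dosing occasions a day for 16 weeks give 16 x 7 x 2 = 224 nominal occasions. The floor is 0.80 x 224 = 179.2. A ceiling at 120% would be 1.20 x 224 = 268.8. The plan has the first and not the second.

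**4. Whether another rule closes the gap.**

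- The BSA, PASI and IGA items concern disease severity, not intake.
- SAP Section 5.3.1.2.6 also removes participants who stopped for other reasons (intercurrent event 3) without completing dosing before Week 16. An over-taker who stays on treatment is not among them.
- SAP Appendix 4 (Section 6.4) includes wrong treatment or incorrect dose among major deviations, but only summarises and lists them. It does not tie them to per-protocol membership.
- SAP Appendix 2 records no changes to the protocol-planned analyses, so the omission is not declared as a deliberate departure.

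**5. What the set feeds.** SAP Section 5.3.1.2.6 uses it for the pairwise analysis of PASI 75 at Week 16. Section 5.3.1.2.3.1 defines that as each active arm against placebo. The gMCP-Mod primary analysis (Section 5.3.1.2.3) uses the full analysis set.

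**The case against.** The best reply is that over-takers are already partly handled. Protocol Section 6.4 allows treatment to be stopped for poor adherence, Section 7.1 lists inability to comply with protocol requirements as a reason for discontinuation, and Section 7.2 withdraws participants who do not comply. Anyone stopped that way before completing dosing leaves the per-protocol set through Section 5.3.1.2.6. Those who remain are still visible in the band above 120% and, where classed as such, among the major deviations. This stands as a limit on the point: only over-takers who continue treatment are kept. Being visible in a table, however, does not remove them from the set.

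A second reply is that a tablet-count ceiling does not reproduce the protocol's rule. The protocol requires the investigator to judge the excess intentional or repeated, the boundary differs at exactly 120%, and tablets that are simply not returned can inflate the ratio. This also stands. It is why the fix needs the investigator's judgement as well as the ratio.

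A third reply is that the protocol describes this population only as generally compliant and uses it for sensitivity analysis. That limits the importance of the point. It does not reconcile a set described as compliant with members labelled significantly noncompliant.

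**Conclusion.** The point holds as a mismatch between SAP Table 3 and Protocol Section 6.4. Every participant who otherwise qualifies and stays on treatment with a ratio above 1.20 is kept. The consequence is confined to the supporting per-protocol comparisons with placebo; the primary analysis does not change. How far those comparisons would move cannot be estimated, because the documents give no rate of over-taking.

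A reader might infer more, and the documents do not support it.

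- **Fasting.** Protocol Section 2.2 says "Based on the interim food effect data from protocol 77242113PSO1003, study intervention should be administered under fasted conditions" and Section 4.1 adds "Dietary intake should be recorded per study manual", so a fasting criterion may seem equally missing. The recording is left to a study manual that is not supplied, and per-dose diet data are not shown to exist. A criterion on active doses would be undefined for placebo and would make membership depend on arm. Before Amendment 2, dosing with food was allowed, so those doses cannot be counted as violations.
- **QD against BID.** Evening food might seem to penalise only the BID arms, since the evening tablet in the QD arms is placebo. That assumes no food with morning doses. If fractions g of morning and f of evening doses are taken with food, and food cuts a dose's exposure by r, QD loses g x r and BID loses 0.5 x (g + f) x r. With assumed values f = g = 30% and r = 50%, both lose 15%. With g = 30% and f = 0, QD loses 15% and BID 7.5%, so the direction reverses. The documents give none of f, g or r, and the per-protocol analysis makes no QD-versus-BID comparison.
- **PK samples.** SAP Section 5.7.1.2 excludes a sample after "incorrect or skipped dose(s) based on 2 previous doses prior to the PK sample collection". The word incorrect is not defined and could cover a dose taken with food, so an omission is not established.
- **Safety-withheld doses.** The SAP denominator counts tablets that were due, which can be read as already leaving out withheld ones. A conflict with the protocol's exemption is not shown.

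**What to change.** In SAP Table 3, replace the floor of 80% with 80% to 120%, using the middle band of Appendix 7. Add a separate criterion excluding participants whom the investigator judged significantly noncompliant for over-taking under Protocol Section 6.4; this also covers the boundary case at exactly 120%. Settle the rule and the resulting membership before unblinding.

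The change needs SAP wording and programming on tablet counts already planned for Appendix 7, plus a record of the investigator's judgement. Protocol Section 6.3 lists accountability data as potentially unblinding, so membership should be derived under the same safeguards. The per-protocol set becomes slightly smaller, and some participants may be dropped only because tablets were not returned. A review of ratios above 120% before unblinding, checking for unreturned tablets, would limit that.
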